6.1.1.2 Inclusion/Exclusion Criteria

All inclusion and exclusion criteria will be reviewed by the investigator or qualified designee to ensure that the subject qualifies for the trial.

6.1.1.3 Medical History

A medical history will be obtained by the investigator or qualified designee. Medical history will include all active conditions, and any condition diagnosed within the prior 10 years that are considered to be clinically significant by the Investigator. Details regarding the disease for which the subject has enrolled in this study will be recorded separately and not listed as medical history.

6.1.1.4 Prior and Concomitant Medications Review

6.1.1.4.1 **Prior Medications**

The investigator or qualified designee will review prior medication use, including any protocol-specified washout requirement, and record prior medication taken by the subject within 28 days before starting the trial.

Treatment for the disease for which the subject has enrolled in this study will be recorded separately and not listed as a prior medication.

6.1.1.4.2 Concomitant Medications

The investigator or qualified designee will record medication, if any, taken by the subject during the trial.

6.1.1.5 Disease Details and Treatments

6.1.1.5.1 Disease Details

The investigator or qualified designee will obtain prior and current details regarding disease status.

6.1.1.5.2 **Prior Treatment Details**

The investigator or qualified designee will review all prior cancer treatments including systemic treatments, radiation and surgeries.

6.1.1.5.3 Subsequent Anti-Cancer Therapy Status

The investigator or qualified designee will review all new anti-neoplastic therapy initiated after the last dose of trial treatment. If a subject initiates a new anti-cancer therapy within 30 days after the last dose of trial treatment, the 30 day Safety Follow-up visit must occur before the first dose of the new therapy. Once new anti-cancer therapy has been initiated the subject will move into survival follow-up.

6.1.1.6 Adverse Event (AE) Monitoring

The investigator or qualified designee will assess each subject to evaluate for potential new or worsening AEs as specified in the Trial Flow Chart and more frequently if clinically indicated. Adverse experiences will be graded and recorded throughout the study and during the follow-up period according to NCI CTCAE Version 4.0. Toxicities will be characterized in terms regarding seriousness, causality, toxicity grading, and action taken with regard to trial treatment.

6.1.1.7 Full Physical Exam

The investigator or qualified designee will perform a complete physical exam during the screening period. Clinically significant abnormal findings should be recorded as medical history.

12-Lead Electrocardiogram (ECG)

A standard 12-lead ECG will be performed using local standard procedures once at screening. Clinically significant abnormal findings should be recorded as medical history. Additional time points may be performed as clinically necessary.

6.1.1.8 Directed Physical Exam

For cycles that do not require a full physical exam per the Trial Flow Chart, the investigator or qualified designee will perform a directed physical exam as clinically indicated prior to trial treatment administration.

6.1.1.9 Vital Signs

The investigator or qualified designee will take vital signs at screening, prior to the administration of each dose of trial treatment and at treatment discontinuation as specified in the Trial Flow Chart (Section 6.0). Vital signs should include temperature, pulse, respiratory rate, weight and blood pressure. Height will be measured at screening only.

6.1.1.10 Eastern Cooperative Oncology Group (ECOG) Performance Scale

The investigator or qualified designee will assess ECOG status at screening, prior to the administration of each dose of trial treatment and discontinuation of trial treatment as specified in the Trial Flow Chart.

6.1.1.11 Tumor Imaging and Assessment of Disease

For this study, imaging of chest abdomen, and pelvis are required at Screening and at each scheduled disease assessment visit after enrollment. Computed tomography (CT) is the modality strongly preferred for chest. For abdomen and pelvis CT or magnetic resonance imaging (MRI) are both acceptable. However, the same imaging modality and technique, such as use of contrast should be used consistently for an anatomic region in a subject throughout the trial. At Screening, imaging scans must be performed within 28 days prior to date of allocation to confirm the subject has measurable disease per RECIST 1.1. After that tumor evaluation should be performed after 6 weeks (end of cycle 2), 12 weeks (end of cycle 4), and every 12 weeks thereafter. Imaging assessments should continue until disease progression per RECIST 1.1. The Trial Flow Chart - Section 6.0 summarizes the trial procedures to be performed at each visit.

6.1.1.12 End of Treatment and Follow-up Tumor Imaging

In subjects who discontinue trial treatment without documented disease progression, every effort should be made to continue monitoring their disease status by tumor imaging using the same imaging schedule used while on treatment (after 6 weeks (end of cycle 2), 12 weeks (end of cycle 4), and every 12 weeks (+/- 14 days) thereafter) to monitor disease status until the start of new anti-cancer treatment, disease progression, death, or the end of the study, whichever occurs first.

ASSESSMENTS DURING TREATMENT

7.0 EVALUATION CRITERIA

7.1 Objective Response

The major parameters of response to be assessed include complete and partial responses, Progression-Free Survival, Overall Survival, documentation of Sites of Recurrence, and Treatment Related Toxicity. Treatment response will be based on RECIST v1.1 Guidelines for Measurable Lesions.

Measurable Lesions- Only recurrent patients with measurable lesions will be enrolled in the study. All target lesions must be assessed using the same technique as baseline. Included in the evaluations are the following standard response criteria for target lesions:

- Complete Response (CR): Disappearance of all target lesions. No new lesions. Lymph nodes must be <10mm short axis.
- Partial Response (PR): At least a 30% decrease in the sum of the longest diameter of target lesions, taking as reference the baseline sum of the longest diameters. No new lesions.
- Progressive Disease (PD): The appearance of a new lesion, or at least a 20% increase in the sum of the longest diameters of the target lesions, taking as the reference the smallest sum of the longest diameters recorded since treatment started, and at least 5mm increase.
- Stable Disease (SD): Target lesions do not qualify for CR, PR, or progression. No new lesions.

All non-target lesions must be assessed using the same technique as baseline. Included in the evaluations are the following standard response criteria for non-target lesions:

- Complete Response: The disappearance of all non-target lesions.
- Incomplete Response/Stable Disease: The persistence of one or more non-target lesion(s).
- Progression Disease: The appearance of one or more new lesions and/or unequivocal progression of existing non-target lesions.

Objective Response (OR) will be defined as Complete or Partial Response using CR or PR as described by the above RECIST v1.1 Response Criteria.

Progression-Free Survival (PFS) will be defined as date from entry to a particular protocol to date of reappearance or increasing parameters of disease on imaging (CT scan or MRI) or by clinical exam or death from any cause, or is censored at date of last disease assessment.

Overall Survival (OS) will be defined as observed length of life from entry to a particular protocol to death or, for living patients, date of last contact.

Treatment Toxicity: The grade level of the various toxicities will be classified using the Common Toxicity Criteria, version 4 (CTC, v.4) guidelines. Acute toxicities will be scored if occurring </= 30 days from treatment completion, and chronic if > 30 days. Frequency and duration of treatment interruptions due to the treatment toxicity will be assessed.

8.0 STUDY MONITORING AND REPORTING PROCEDURES

8.1 Personnel responsible for the safety review and its frequency:

The principal investigator will be responsible for monitoring the data, assuring protocol compliance, and conducting the safety reviews at the specified frequency which must be conducted at a minimum of every 6 months (including when reapproval of the protocol is sought). During the review process, the principal

investigator with the help of the Remote Monitoring Coordinator will evaluate whether the study should continue unchanged, require modification/amendment, or close to enrollment. Either the principal investigator, the IRB or the Yale Cancer Center Data and Safety Monitoring Committee (DSMC) have the authority to stop or suspend the study or require modifications.

8.2 The risks associated with the current study are deemed moderate for the following reasons:

- 1. We do not view the risks associated with pembrolizumab as minimal.
- 2. Given the now established safety and validity of studies performed using the FDA-approved drug pembrolizumab, we do not view the proposed study as high risk.

Although we have assessed the proposed study as one of moderate risk, the potential exists for anticipated and/or unanticipated adverse events, serious or otherwise, to occur since it is not possible to predict with certainty the absolute risk in any given individual or in advance of first-hand experience with the proposed study methods. Therefore, we provide a plan for monitoring the data and safety of the proposed study as follows:

8.3 Attribution of Adverse Events:

Adverse events will be monitored for each subject participating in the study and attributed to the study procedures / design by the principal investigator [name], according to the following categories:

a.) Definite: Adverse event is clearly related to investigational procedures(s)/agent(s).

- b.) Probable: Adverse event is likely related to investigational procedures(s)/agent(s).
- c.) Possible: Adverse event may be related to investigational procedures(s)/agent(s).
- d.) Unlikely: Adverse event is likely not to be related to the investigational procedures(s)/agent(s).
- e.) Unrelated: Adverse event is clearly not related to investigational procedures(s)/agent(s).

8.4 Plan for Grading Adverse Events:

The following scale will be used in grading the severity of adverse events noted during the study:

- 1. Mild adverse event
- 2. Moderate adverse event
- 3. Severe

8.5 Plan for Determining Seriousness of Adverse Events:

An adverse event may be graded as severe but still not meet the criteria for a Serious Adverse Event. Similarly, an adverse event may be graded as moderate but still meet the criteria for an SAE. It is important for the PI to consider the grade of the event as well as its "seriousness" when determining whether reporting to the IRB is necessary.

8.6 Plan for reporting Reportable Adverse Events and other unanticipated problems involving risks to subjects or others to the IRB

The principal investigator will report the following types of events to the IRB: a) adverse events that are serious or life-threatening AND unanticipated (or anticipated but occurring with a greater frequency than expected) AND possibly, probably or definitely related to the drug/device/intervention; and b) other unanticipated problems involving risks to subjects or others.

These adverse events or unanticipated problems involving risks to subjects or others will be reported to the IRB in accordance with IRB Policy 710, using the appropriate forms found on the website.

Plan for reporting adverse events to co-investigators on the study, as appropriate the protocol's research monitor(s), e.g., Yale Cancer Center Data and Safety Monitoring Committee (DSMC), Protocol Review Committee (PRC), DSMBs, study sponsors, funding and regulatory agencies, and regulatory and decision-making bodies.

For the current study, the following individuals, funding, and/or regulatory agencies will be notified (choose those that apply):

- X All Co-Investigators listed on the protocol.
- X Yale Cancer Center Data and Safety Monitoring Committee (DSMC)
- X Merck Pharmaceuticals

The principal investigator [name] will conduct a review of all adverse events upon completion of every study subject. The principal investigator will evaluate the frequency and severity of the adverse events and determine if modifications to the protocol or consent form are required.

8.7 Definition of an Overdose for This Protocol and Reporting of Overdose to the Sponsor

For purposes of this trial, an overdose will be defined as any dose exceeding the prescribed dose of 1,000 mg or greater (\geq 5 times the indicated dose). No specific information is available on the treatment of overdose of pembrolizumab. In the event of overdose, pembrolizumab should be discontinued and the subject should be observed closely for signs of toxicity. Appropriate supportive treatment should be provided if clinically indicated.

If an adverse event(s) is associated with ("results from") the overdose of Sponsor's product or vaccine, the adverse event(s) is reported as a serious adverse event, even if no other seriousness criteria are met. If a dose of Sponsor's product or vaccine meeting the protocol definition of overdose is taken without any associated clinical symptoms or abnormal laboratory results, the overdose is reported as a non-serious Event of Clinical Interest (ECI), using the terminology "accidental or intentional overdose without adverse effect." All reports of overdose with and without an adverse event must be reported by the investigator within 24 hours to the Sponsor either by electronic media or paper.

8.8 ADVERSE EVENT REPORTING

This study will utilize the CTC version 4.0 for toxicity and Adverse Event Reporting. A copy of the CTC version 4.0 can be downloaded from the CTEP home page (Table 7).

Toxicity Grade	Type ^a	Local IRB	Study Coordinators
			Via email/fax/phone

4,5	Unknown	Yes	Yes
5	Known	No	Yes*
2,3	Unknown	No	No
4 (non-myelo)	Known	No	No
4 (myelo ^b)	Known	No	No

* If clearly related to the commercial agent(s)

^a Type (Known or unknown) is based on toxicities included in the package insert or literature of known toxicities associated with the study drug(s).

^b Myelosuppression, which includes neutropenia, anemia, thrombocytopenia

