8.9.5 Assessment of Adverse Events

All AEs and SAEs whether volunteered by the subject, discovered by study personnel during questioning, or detected through physical examination, laboratory test, or other means will be reported appropriately.

Each reported AE or SAE will be described by its duration (i.e., start and end dates), regulatory seriousness criteria if applicable, suspected relationship to pembrolizumab (see following guidance), and actions taken.

To ensure consistency of AE and SAE causality assessments, investigators should apply the following general guideline:

Yes

There is a plausible temporal relationship between the onset of the AE and administration of pembrolizumab and the AE cannot be readily explained by the subject's clinical state, intercurrent illness, or concomitant therapies; and/or the AE follows a known pattern of response to pembrolizumab and/or the AE abates or resolves upon discontinuation of pembrolizumab or dose reduction and, if applicable, reappears upon re-challenge.

No

Evidence exists that the AE has an etiology other than pembrolizumab (e.g., preexisting medical condition, underlying disease, intercurrent illness, or concomitant medication); and/or the AE has no plausible temporal relationship to pembrolizumab administration (e.g., cancer diagnosed 2 days after first dose of study drug).

Expected adverse events are those adverse events that are **listed** or characterized in the Package Insert or current Investigator Brochure.

Unexpected adverse events are those **not listed** in the Package Insert (P.I.) or current Investigator Brochure (I.B.) or not identified. This includes adverse events for which the specificity or severity is not consistent with the description in the P.I. or I.B. For example, under this definition, hepatic necrosis would be unexpected if the P.I. or I.B. only referred to elevated hepatic enzymes or hepatitis.

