8.10.2 Specific Instructions for Recording Adverse Events

Investigators should use correct medical terminology/concepts when reporting AEs or SAEs. Avoid colloquialisms and abbreviations. All information will be recording using Oncore Clinical Trials Management System.

a. Diagnosis vs. Signs and Symptoms

If known at the time of reporting, a diagnosis should be reported rather than individual signs and symptoms (e.g., record only liver failure or hepatitis rather than jaundice, asterixis, and elevated transaminases). However, if a constellation of signs and/or symptoms cannot be medically characterized as a single diagnosis or syndrome at the time of reporting, it is ok to report the information that is currently available. If a diagnosis is subsequently established, it should be reported as follow-up information.

b. Deaths

All deaths that occur during the conduct of the research must be reported to the Yale Principal Investigator and the Remote Monitoring Coordinator immediately (if possible) to ensure that all over site committees are properly informed. All information will be entered into Oncore Clinical Trials Management System and updated appropriately. Further determination regarding the need to submit to the subjects local IRB, Yale University HHRP following IRB Policy 710 for reporting Unanticipated Problems Involving Risk to Subjects and Merck Pharmaceuticals, Inc. Drug Safety Committee will be

reviewed.

When recording a death, the event or condition that caused or contributed to the fatal outcome should be reported as the single medical concept. If the cause of death is unknown and cannot be ascertained at the time of reporting, report "Unexplained Death".

c. Preexisting Medical Conditions

A preexisting medical condition is one that is present at the start of the study. Such conditions should be reported as medical and surgical history.

A preexisting medical condition should be re-assessed throughout the trial and reported as an AE or SAE only if the frequency, severity, or character of the condition worsens during the study. When reporting such events, it is important to convey the concept that the preexisting condition has changed by including applicable descriptors (e.g., "more frequent headaches").

d. Hospitalizations for Medical or Surgical Procedures

Any AE that results in hospitalization or prolonged hospitalization should be documented and reported as an SAE.

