9.2 SUB SITE INVESTIGATOR SAE REPORTING REQUIREMENTS

The collaborating investigator (Sub Site PI) in a multi-center trial will report **serious**, **unexpected** adverse events occurring at their site to the Yale Principal Investigator **regardless of attribution** immediately (if possible) of knowledge of the event. Full written reports should be submitted to the Yale PI within 5 calendar

days of initial knowledge of the report. This information will also need to be recorded in Oncore Clinical Trials Management System in the SAE section.

Send SAEs to the Yale Principal Investigator:

Name: [name] [contact] Email: [contact] [contact]

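### Table 7 sets adverse event reporting by grade and Known/Unknown type alone, and conflicts with the protocol's own rules for unexpected serious events, deaths and expectedness

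*Combined protocol and SAP*

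**What the plan says.** Table 7 (section 8.8) has two recipients, the local IRB and the study coordinators, and two inputs, CTC grade and whether the toxicity is Known or Unknown. Two of its rows matter here. The row for unexpected events of moderate or severe grade reads "2,3 Unknown No No". The row for a Grade 5 Known event gives No for the IRB and a starred Yes for the coordinators; the star means "If clearly related to the commercial agent(s)". Footnote a bases Known or Unknown on the package insert or on literature about the drug's toxicities.

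Other sections use different triggers:

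- Section 8.5 separates grade from seriousness: "an adverse event may be graded as moderate but still meet the criteria for an SAE". It asks the principal investigator to weigh both when deciding on IRB reporting.
- Section 8.6 sends to the IRB "adverse events that are serious or life-threatening AND unanticipated (or anticipated but occurring with a greater frequency than expected)", provided they are at least possibly related. Section 9.1 uses much the same test for expedited reporting. Neither has a grade threshold.
- Section 9.2 has sub-sites report serious, unexpected "adverse events occurring at their site to the Yale Principal Investigator", whatever the attribution.
- Section 8.10.2(b) states: "All deaths that occur during the conduct of the research must be reported to the Yale Principal Investigator and the Remote Monitoring Coordinator immediately".
- Section 8.9.5 calls an event unexpected if it is not listed "in the Package Insert (P.I.) or current Investigator Brochure (I.B.) or not identified", or if its specificity or severity does not fit the listing.

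**The concern.** A grade-by-type grid is the part of a safety section that site staff are most likely to work from, and this one never asks whether the event is serious. An unlisted immune toxicity that puts a patient in hospital at Grade 3 is No and No in Table 7, yet it is reportable under 8.6 and 9.1 if at least possibly related. A death from a listed toxicity that is rated probable falls outside the starred condition, yet 8.10.2(b) covers it.

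The trial is multi-site, and section 8.1 gives the principal investigator, the IRB and the DSMC authority to stop, suspend or modify it. Two sites could handle the same event differently while each followed one section of the protocol. The events at risk of late or missing notice are among those that such oversight most needs to see.

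**Working it through.** No arithmetic applies and the plan gives no figure to reproduce. The check sets each Table 7 rule beside the sections that govern the same event.

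1. **Serious, unexpected, possibly related event at Grade 2 or 3.**
   - Table 7: IRB No, coordinators No.
   - The seriousness definition in 9.1 rests on outcome and includes inpatient hospitalization, so a Grade 2 or 3 event can qualify. Section 8.5 says the same of a moderate event.
   - Section 8.6 sends the event to the IRB. Section 9.1 requires expedited handling. If it occurs at a sub-site, 9.2 sends it to the Yale principal investigator.
   - Result: direct conflict in the IRB column.

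2. **Unexpected Grade 2 or 3 event that is not serious.**
   - Table 7: No and No.
   - Sections 8.6, 9.1 and 9.2 do not ask for expedited reporting of it.
   - Result: no conflict. The problem is confined to serious events.

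3. **Death from a known toxicity, coordinator column.**
   - Table 7: notice only if clearly related. Section 8.3 has five attribution levels and uses those words for the top one: "Definite: Adverse event is clearly related to investigational procedures(s)/agent(s)". Three levels are at least possibly related (Definite, Probable, Possible). The star matches one of them, which leaves 3 − 1 = 2 outside it.
   - Section 8.10.2(b): all deaths, immediately, with no condition on relatedness. Section 8.9.1 also lists all deaths among the events to be reported.
   - Result: conflict over when a death triggers notice. The recipients are the study coordinators in one place and the Remote Monitoring Coordinator in the other, and no section says that these are the same role.

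4. **Death from a known toxicity, IRB column.**
   - Table 7: No.
   - Section 8.10.2(b) leaves submission to the IRB for further determination.
   - Result: no contradiction by itself.

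5. **Event described in the literature but not in the package insert or Investigator Brochure.**
   - Footnote a: Known.
   - Section 8.9.5: unexpected.
   - A second mismatch follows from severity. A listed toxicity that is worse than its listing is unexpected under 8.9.5, while footnote a says nothing about severity.
   - Result: the same event can fall on opposite sides of the expectedness test.

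6. **Does any text settle which rule governs?** Section 8.9.2 refers serious adverse events to Section 9, and 8.9.3 makes the investigator responsible for reporting events as outlined there. Table 7 carries no cross-reference and is not limited to non-serious events. It has Grade 5 entries, and death is always serious under 9.1. The referral to Section 9 therefore helps with item 1 but does not remove the conflicting entry, and it leaves items 3 and 5 open.

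**The case against.** The strongest reply is that the protocol already routes serious events elsewhere. Sections 8.9.2 and 8.9.3 point to Section 9. Section 8.6 marks the co-investigators, the DSMC and the drug manufacturer for notification, and has the principal investigator review all adverse events as each subject completes. Section 9.2 covers sub-sites, and 9.3 covers the manufacturer. On that reading Table 7 is a grade-based aid that no careful site would let override Section 9. This stands as a limit on the consequence: a report is missed or delayed only where a site relies on Table 7. It does not make the entries consistent.

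A reader might infer more than the documents support:

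- **That these events reach nobody.** This is true only of Table 7's two columns; the other routes remain.
- **That 8.6, 9.1 and 9.2 all require reporting of deaths from known toxicities.** In general they do not. Sections 8.6 and 9.1 reach such a death if frequency exceeds expectation, and 8.9.5 can make one unexpected on severity. Otherwise the death conflict rests on 8.10.2(b), supported by 8.9.1.
- **That the primary toxicity endpoint is compromised.** Section 11.2 evaluates all treated patients for toxicity, and 11.4 has adverse events recorded on Adverse Events Forms. Neither depends on Table 7 notices.
- **That 9.2 sends every serious event to the lead investigator.** It covers serious events that are also unexpected.

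**Conclusion.** The point holds as an internal inconsistency in safety reporting, in three places: the double No for Grade 2-3 Unknown events when the event is serious; the relatedness condition on notice of a Grade 5 Known event; and the reference used for expectedness. The first is the clearest, because the IRB entry contradicts 8.6 outright when the event is serious and at least possibly related.

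The size cannot be put as a count. The documents give no rate of such events, and accrual is at most 25 patients. Error rates, sample size and the toxicity tabulation are untouched.

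The second item rests on reading the starred condition through 8.3, whose wording it shares; 8.9.5 has a separate Yes/No causality scale. It also stops short of equating the study coordinators with the Remote Monitoring Coordinator. The practical consequence assumes that some site staff would work from Table 7 alone. The documents neither confirm nor exclude this. The correction is nonetheless worth making, because it is cheap and concerns safety oversight.

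**What to change.** - In 8.8, state that Table 7 applies to non-serious events only, and that serious events of any grade follow 8.6 and Section 9: serious unexpected events at sub-sites to the Yale principal investigator under 9.2, and to the IRB when 8.6 or 9.1 is met. The Grade 5 entries must then come out, since death is always serious. The alternative is to delete the table and refer to Section 9.
- State that all deaths follow 8.10.2(b), and remove the clearly related condition. Say whether the study coordinators and the Remote Monitoring Coordinator are the same role.
- If Table 7 is kept, rewrite footnote a to use the 8.9.5 definition: package insert or current Investigator Brochure, with an event unexpected when its specificity or severity does not fit the listing.

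The cost is a wording amendment to one table and its footnotes, and possibly a few more notifications. No procedures, visits or patients are added.
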